4.2.2. Efficacy analyses

4.2.2.1. Best overall response (BOR)

Number and percentage of patients within a particular best overall response (BOR) category will be provided for the following patients in separate tables: R/R NHL phase 1 patients, R/R CLL phase 1 patients, R/R MCL patients (phase 1 and phase 2 combined) and R/R CLL patients (phase 2 only). In addition, numbers and percentages of BOR by disease group (MCL, non-GCB DLBCL, FL, SLL) for phase 1 R/R NHL patients as well as for phase 2 R/R CLL patients with del 17p will be presented in separate additional tables.

For R/R NHL(MCL,non-GCB DLBCL, FL, SLL) patients, the response categories are (CR, PR, SD, PD) and assessments are based on the Lugano criteria. For R/R CLL patients, these are (CR, CRi, nPR, PR, PRL, SD, PD) and assessments are based on iwCLL 2018 criteria. For R/R NHL phase 1 and R/R CLL phase 1, tables with responses based on investigator assessments will be presented. For R/R MCL patients (phase 1 and phase 2 combined) and R/R CLL patients (phase 2) separate tables for assessments by investigator and BICR will be created.

For R/R NHL phase 1 and R/R CLL phase 1, investigator-assessed BOR will be listed separately. For R/R MCL patients (phase 1 and phase 2 combined) and R/R CLL patients (phase 2) separate listings with investigator-assessed BOR and BICR-assessed BOR will be presented.

The analysis will be based on the tumor response set.

4.2.2.2. Overall response rate (ORR)

Primary analysis of BICR-assessed ORR will be conducted on the tumor response analysis set for MCL patients (phase 1 and phase 2 combined) and R/R CLL patients (phase 2) separately. ORR and the corresponding 95% two-sided CI of ORR will be presented based on Clopper-Pearson exact method. BICR-assessed ORR+PRL and the corresponding 95% two-sided Clopper-Pearson CI will also be presented.

.For MCL patients (phase 1 and phase 2 combined), maximum percentage changes from baseline in the sum of product diameters (SPD) will be presented using waterfall plots (tumor response marked with different colors) based on BICR assessments.

Analysis of investigator-assessed ORR, ORR+PRL and SPD will be conducted on the tumor response analysis set using same statistical methods. The concordance between investigator-assessed and BIRC-assessed ORR as well as CR and PR rates will be summarized for MCL cohort. The concordance between investigator-assessed and BIRC-assessed ORR, CR or CRi rate and ORR+PRL rate will be summarized for CLL cohort.

Subgroup analysis

Additionally, subgroup analysis following the categories as below will be performed where deemed appropriate, these will be summarized and presented on a forest plot including the BICR-assessed ORR and 95% CI.

- Age at enrolment (<65 versus ≥ 65 ; <75 versus ≥ 75)
- Sex (male versus female)
- ECOG (0 versus 1 versus ≥ 2)
- Bulky disease (longest diameter of lymph node <5 cm vs. ≥ 5 cm and <10 cm vs ≥ 10 cm at baseline)
- Number of previous lines (1 versus 2 versus ≥ 3)
- Extranodal disease (yes versus no) – MCL only
- Bone marrow involvement (yes versus no) – MCL only
- Gastrointestinal disease (yes versus no) – MCL only
- Simplified MCL international prognostic index (MIPI) (low risk [0-3] vs intermediate risk [4-5] vs high risk [6-11]) – MCL only
- Refractory disease at baseline (yes versus no)
- Ann Arbor lymphoma staging (1-3 versus 4) -MCL only
- Rai staging at baseline (0-II versus III-IV) - Phase 2 cohort B only
- $\beta 2$ -microglobulin at baseline (≤ 3.5 mg/L vs. >3.5 mg/L) – Phase 2 cohort B only
- IGHV mutation (mutated versus unmutated) – Phase 2 cohort B only
- 17p deletion (yes versus no) – Phase 2 cohort B only
- 11q deletion (yes versus no) – Phase 2 cohort B only
- TP53 mutation (mutated versus unmutated) - Phase 2 cohort B only

In addition, same the subgroup analysis will be presented for the investigator assessed ORR.

4.2.2.3. Tumor response by visit

Time windows will be used to ensure tumor response data recorded at any time point has the potential to be summarized, for details refer to section 4.2.3.1.

Both BICR and investigator tumor response data will be summarized by visit using time windows for the phase 2 R/R CLL cohort only. Investigator-assessed tumor response for R/R NHL phase 1 patients, R/R CLL phase 1 patients, R/R MCL patients (phase 1 and phase 2 combined) and phase 2 R/R CLL patients at each timepoint will be presented in listings and swimmer plots. BICR-assessed tumor response by timepoint will be presented in listings and swimmer plots for R/R MCL patients (phase 1 and phase 2 combined) and phase 2 R/R CLL patients.

4.2.2.4. Duration of response (DoR)

The analysis of BICR-assessed DoR will be estimated using the Kaplan-Meier (KM) methods will be performed on R/R MCL patients (phase 1 and phase 2 combined) and phase 2 R/R CLL patients separately. KM estimates will be calculated for event time quartiles (including median, Q1 and Q3), and event-free rates will be calculated at selected time points (i.e. 6 months, 12 months, 18 months).

In addition, type of event (i.e. death, PD) and the reason for censoring (i.e. data cutoff, lost to follow-up, subsequent anticancer therapy) will be summarized in the same table. Please refer Table 5 for censoring rules.

Kaplan-Meier plot for duration of response will be created accordingly. In addition, Kaplan-Meier plot for duration of response by best overall response (PR and CR) will be developed in a separated plot.

The analysis will be performed on the tumor response set.

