Abbreviations: ALT = alanine aminotransferase; AST = aspartate aminotransferase; anti-HBc = hepatitis B core antibody; anti-HBs = hepatitis B surface antibody; BID = twice daily; CR = complete remission (response); CT = computed tomography; ECG = electrocardiogram; ECOG = Eastern Cooperative Oncology Group; FISH = fluorescence in situ hybridization; HBsAg = hepatitis B surface antigen; HBV = hepatitis B virus; HCV = hepatitis C virus; HIV= human immunodeficiency virus; Hgb = hemoglobin level; IGHV = immunoglobulin heavy-chain variable; IHC = immunohistochemistry; INR = international normalized ratio; IVIG = intravenous immunoglobulins; MRD=minimal residual disease; NK=Natural killer; PCR = polymerase chain reaction; PET = positron-emission tomography; PK = pharmacokinetic; PLT = platelet count; PO = oral; PR= Partial response; Q12W = every 12 weeks; Q24W = every 24 weeks; QM = every month; EoT =End of Treatment.

Footnotes (Phase 2- CLL cohort)

- Screening tests should be performed within 28 days before the first administration of study drug, unless otherwise indicated.
- Subjects will have visits on Days 1, 8 and 15 of Cycle 1, on Days 1 and 15 of Cycles 2 to 6, on Day 1 of Cycle 7, and on Day 1 of every third cycle thereafter, starting with Cycle 10; each cycle is 28 days.

- c. End of treatment (EoT) visit is required for subjects who permanently discontinue treatment early for any reason, including disease progression. (except for death, lost to follow up or withdrawal of consent). The EoT visit should be performed within 7 days of the last dose of study drugs, if possible, and is not required for subjects who discontinue from study treatment within 10 days of a scheduled study visit or if the EoT visit would be performed within 14 days of the SFU visit. A 30-day (+ 7 days) safety follow-up visit (SFU) is required for all subjects at 30 (+ 7) days after last dose of study drug to monitor for resolution or progression of AEs and to document the occurrence of any new events, regardless of whether the subject receives a new anticancer therapy or demonstrates disease progression within this timeframe.

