8.1.1.2 CLL tumor assessment

Overall response assessments for CLL subjects will be based upon evaluation of physical exams, recording of symptoms, radiologic evaluations, and hematologic evaluations per the Schedule of Activities. Subjects who have signs and symptoms of disease progression outside of the scheduled study visits and assessments should be evaluated by the Investigator with a physical exam and a CBC with differential to determine if disease progression is present. The blood samples for response or disease progression determination should be confirmed by a central laboratory (not applicable for Phase 1 CLL subjects; samples from local laboratories can be used if central testing is unavailable). Any suspected case of disease progression (in the absence of laboratory or histopathologic changes meeting the criteria for PD) should be confirmed with a CT scan and should be reported to the Sponsor or designee. In addition,

when clinically appropriate, based on Investigator-perceived risk-benefit assessment, a subject may continue treatment and remain under close observation until progression is confirmed. New anticancer therapy should be withheld if clinically appropriate in the absence of confirmed progressive disease.

Baseline:

For baseline, a CT scan with contrast (MRI should be used if contraindicated) is required to cover the neck, chest, abdomen, and pelvis and any other disease sites (e.g. brain), within 28 days before the first dose of study drug. Spleen and liver size should be recorded in CT measurement. Additionally, bone marrow aspiration and biopsy within 3 months before first dose of study drug is required. Physical exam (especially lymph node and organomegaly), B symptoms, blood counts with differential and other clinical information should be recorded in the eCRF at the baseline. PET-CT is not required, but if performed within 60 days before the study treatment, should be recorded in eCRF.

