There must be radiographically measurable disease at screening (have ≥ 1 nodal lesion >2.0 cm in the longest diameter). Up to 6 measurable disease (only nodal lesions ≥ 1.5 cm in the longest diameter, clearly measurable in 2 perpendicular dimensions, clearly measurable in 2 perpendicular dimensions), will be followed as target lesions for each subject. Measurable sites of disease should be chosen such that they are representative of the subject's disease. In addition, selection of target lesions should be from as disparate regions of the body as possible when these areas are significantly involved. Target lymph nodes should not be selected from previously irradiated areas. If the sole measurable lesion lies within the field of prior radiotherapy, there must be evidence of disease progression in that lesion that has not been previously irradiated. If additional lesions are present but are not included in the target lesion assessment, they can be added as non-target lesions followed throughout the study. The cranial-caudal measurement of the spleen and longest diameter of the liver will be assessed at screening and all subsequent response evaluations.

Follow-up:

Radiologic tumor assessment will be performed every 12 weeks (± 7 days) with the first on-treatment radiologic assessment occurring on Cycle 4 Day 1, the second on treatment scan on Cycle 7 Day 1, and so on through Cycle 25, and then every 24 weeks (± 7 days) thereafter. For subjects who achieve a response (CR, CRi, PR, or nPR), CT and overall response assessment must be performed for response confirmation in 12 weeks (± 7 days) after the initial response imaging assessment, and then every 24 weeks (± 7 days) thereafter. Clinical assessments should be done at every visit that physical exam and hematology test are performed.

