3. PRIMARY AND SECONDARY VARIABLES

3.1. Response assessment of NHL(MCL, DLBCL, FL, SLL) and CLL

The efficacy analyses (R/R MCL and R/R CLL subjects) will be based on Blinded Independent Central Review (BICR) assessment and investigator assessment according to relevant response assessment criteria mentioned as below.

Results of this independent review will not be communicated to investigators and the management of patients will be based solely upon the results of the response assessment conducted by the investigator. Please refer section 3.1.3 for more information about BICR assessment. The investigator-assessed visit responses will be used directly for efficacy analyses. The programmatically derived visit responses using investigator assessment may be used for reconciliation purpose only if applicable.

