3.1.2. Response assessment criteria for CLL

The iwCLL criteria (modified from Hallek 2018) (see CSP Table 8) will be used to determine each CLL patient's response at each visit. It will also be used to determine if and when a patient has progressed.

For baseline, a CT scan with contrast (MRI should be used if contraindicated) is required to cover the neck, chest, abdomen, and pelvis and any other disease sites (e.g. brain), within 28 days before the first dose of study drug. Spleen and liver size should be recorded in CT

measurement. Additionally, bone marrow aspiration and biopsy within 3 months before first dose of study drug is required. Physical exam (especially lymph node and organomegaly), B symptoms, blood counts with differential and other clinical information should be recorded in the eCRF at the baseline. PET-CT is not required, but if performed within 60 days before the study treatment, should be recorded in eCRF.

Radiologic tumour assessment will be performed every 12 weeks (\pm 7 days) with the first on-treatment radiologic assessment occurring on Cycle 4 Day 1, the second on treatment scan on Cycle 7 Day 1, and so on through Cycle 25, and then every 24 weeks (\pm 7 days) thereafter. For subjects who achieve a response (CR, CRi, PR, or nPR), CT must be performed for response confirmation in 12 weeks (\pm 7 days) after the initial response imaging assessment, and then every 24 weeks (\pm 7 days) thereafter.

From the investigator's review of the tumour assessment, the tumour response data will be used to determine each patient's visit response according to iwCLL criteria (Hallek 2018). At each visit, patients will be assigned a iwCLL criteria visit response of CR, CRi, nPR, PR, PRL, SD or PD. If a patient has had a tumour assessment that cannot be evaluated then the patient will be assigned a visit response of not applicable (NA), (unless there is evidence of progression in which case the response will be assigned as PD).

Please refer to Table 3 for the definitions of CR, CRi, nPR, PR, PRL, SD or PD.

Table 3 Response Assessment Criteria for CLL (modified from Hallek 2018) – iwCLL Criteria **

Group	Parameter	CR *	PR #	PD	SD
A	Lymph nodes	None \geq 1.5 cm	Decrease \geq 50% (from baseline) ^a	Increase \geq 50% from baseline or from response	Change of -49% to +49%
	Liver and/or spleen size ^b	Spleen size $<$ 13 cm; liver size normal	Decrease \geq 50% (from baseline)	Increase \geq 50% from baseline or from response	Change of -49% to +49%

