3.3.1.3. Duration of Response (DoR) as assessed by BIRC

DoR is defined as the interval from the first documentation of objective response (PR or better) mentioned above to the earlier of the first documentation of objective disease progression by the BICR or death from any cause.

Subjects who withdraw from the study or are considered lost to follow-up without prior documentation of disease progression will be censored on the date of the last adequate disease assessment. Subjects who start new anticancer therapy before documentation of disease progression will be censored on the date of the last adequate disease assessment that is on or before the start date of the new anticancer therapy.

- For BICR assessments, the date of progression will be determined based on the **earliest** of the scan dates of the component that triggered the progression for the adjudicated reviewer selecting PD or of the reviewer who read baseline first if there is no adjudication for BICR data.
- For investigator assessments, the date of progression will be determined based on the **earliest** of the dates of the component that triggered the progression.
- For both BICR and investigator assessments, when censoring a patient for DoR the patient will be censored at the **latest** of the dates contributing to a particular overall visit assessment.

Table 5 Censoring rules for DoR

Assessment	Outcome	Date of progression or censoring
Documented PD between scheduled visits on or before receiving subsequent anticancer therapy or data cutoff, whichever occurred first	Event	Earliest date of disease assessment documenting progression
Death without documented PD and not receiving subsequent anticancer therapy on or before data cutoff	Event	Date of death
Documented PD or death after subsequent anticancer therapy and the subsequent anticancer started before data cutoff date	Censored	Date of last adequate disease assessment prior to subsequent anticancer treatment
No documented PD or death at the time of data cutoff and subsequent anticancer therapy started before the data cutoff	Censored	Date of last adequate disease assessment prior to subsequent anticancer treatment
Documented PD or death after subsequent anticancer therapy and the subsequent anticancer started after data cutoff date	Censored	Date of last adequate disease assessment on or before data cutoff

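### Are the Cohort B 6-, 12- and 18-month duration-of-response rates at fault because they are read 14 to 18 weeks after the last scheduled CT?

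*SAP*

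**What the plan says.** **Endpoint.** Protocol 9.4.1.3 and SAP 3.3.1.3 start DoR when response is first documented and end it when progression is first documented, or at death. SAP Table 5 dates progression to the earliest assessment that documents it, including assessments between scheduled visits, and dates deaths to the day. For central review, progression takes the earliest "of the scan dates of the component that triggered the progression for the adjudicated reviewer selecting PD".

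**Analysis.** SAP 4.2.2.4 uses Kaplan-Meier, and "event-free rates will be calculated at selected time points (i.e. 6 months, 12 months, 18 months". SAP 4.2.2.5 and 4.2.2.7 carry the method over to PFS and to investigator assessment. The only sensitivity analysis named in the SAP is an optional one on ORR (SAP 2.2).

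**CT schedule.** Protocol 8.1.1.2 says that for responders "CT and overall response assessment must be performed for response confirmation in 12 weeks"; SAP 3.1.2 times this "after the initial response imaging assessment, and then every 24 weeks". The investigator's reading sets the schedule, because "management of patients will be based solely upon the results of the response assessment conducted by the investigator" (SAP 3.1).

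**Checks between CTs.** Protocol 8.1.1.2 adds that "Clinical assessments should be done at every visit that physical exam and hematology test are performed". The Table 3 footnotes place visits, after Cycle 7, "on Day 1 of every third cycle thereafter, starting with Cycle 10", that is, every 12 weeks. Suspected progression "in the absence of laboratory or histopathologic changes meeting the criteria for PD" is to be confirmed by CT.

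**The concern.** A Kaplan-Meier curve on assessment dates drops only when an assessment finds progression. If the last CT was about 16 weeks before the 12-month landmark, nodal progression visible only on CT and arising in those weeks is counted after the landmark. The error has one direction: the rate reads high. Continued 12-weekly CT would leave gaps of only 2.1, 4.2 and 6.3 weeks. Investigator DoR uses the same method and CT schedule, so it is not an independent check. At stake would be a durability figure that looks better than the underlying disease course, with no planned output saying by how much.

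**Working it through.** **1. The plan's own figure.** The documents give no DoR rate. The one stated design figure for Cohort B is 90% power for ORR (n = 60, 70% against 88%, one-sided 2.5%). The smallest rejecting count is 50 of 60: exact alpha 0.0139, power 0.9006. This reproduces, and DoR timing does not enter it.

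**2. Gaps.** With a month of 30.44 days, the landmarks are weeks 26.09, 52.18 and 78.27. When the response CT is DoR week 0, CTs fall at weeks 12, 36, 60 and 84, and clinic visits every 12 weeks.

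| Landmark | Last CT | Gap | Last visit | Gap |
|---|---|---|---|---|
| 26.09 | 12 | 14.1 | 24 | 2.1 |
| 52.18 | 36 | 16.2 | 48 | 4.2 |
| 78.27 | 60 | 18.3 | 72 | 6.3 |

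The CT gaps move by 1 week either way with the CT window.

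**3. Who has these gaps.** Only same-scan responders still on treatment.

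- If central review and the investigator first see response one 12-week scan apart, CTs on the central-review clock fall at weeks 24, 48 and 72, and the gaps are 2.1, 4.2 and 6.3 weeks.
- For responders who stop treatment without progression, the follow-up column of Table 3 is headed every 12 weeks and footnote d says the same. Protocol 7.1.2 says 12 or 24 weeks. Their gaps may be short too.

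**4. Size against unobserved progression.** Assume exponential DoR with true 12-month rate p, so S(t) = p^(t/52.18). CT-only excess: A = S(last CT) − S(landmark). Visit-detected excess: B = S(last visit) − S(landmark). If half is visit-detected, the excess is (A + B)/2.

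At p = 0.85 and 12 months: A = 0.894 − 0.850 = 4.4 points, B = 0.861 − 0.850 = 1.1 points, and the half-and-half value is 2.8 points.

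| p | CT-only, 6/12/18 months | Half at visits |
|---|---|---|
| 95% | 1.4 / 1.5 / 1.7 | 0.8 / 1.0 / 1.1 |
| 85% | 4.1 / 4.4 / 4.6 | 2.4 / 2.8 / 3.1 |
| 70% | 8.5 / 8.2 / 7.8 | 4.8 / 5.1 / 5.2 |

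If 20% of events are deaths dated to the day, multiply by 0.8: at 85%, 1.9 / 2.2 / 2.5.

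**5. Yardstick.** With 53 responders (88% of 60), the 95% half-width is 1.96·√(p(1 − p)/53): 5.9 points at 95%, 9.6 at 85%, 12.3 at 70%. The CT-only limits are also inside these.

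**6. What a remedy would have to work with.** Response is first read at study week 12 (Cycle 4) or 24 (Cycle 7). At the first cut-off, 6 months after the last enrolment, a last-enrolled Cycle 7 responder has 26.1 − 24 = 2.1 weeks of DoR follow-up. With an assumed 60-week enrolment spread, follow-up runs from about 2 to 62 weeks. Simulation then gives about 4 DoR events at 85% and 1.3 at 95%. A Poisson count with mean 1.3 is two or fewer with probability e^(−1.3)(1 + 1.3 + 0.845) = 0.86. A two-parameter Weibull model is barely estimable there, if at all. At the 24-month cut-off the counts are about 14 and 5.

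**The case for a change.** The strongest case for a change is that a confidence interval describes sampling error and is not shifted to allow for an error that always runs one way. Central-review progression is dated by scan, so a clinic finding shortens that gap only if it prompts a CT, and silent nodal growth prompts nothing. Cohort A keeps CT intervals of 12 weeks or less, so the same SAP sentence carries different timing error in the two cohorts. One interval-censored sensitivity analysis looks cheap. In a simulation at the 24-month cut-off (53 responders, 85% rate, exponential truth) it cut 12-month bias from +2.4 to +0.2 points and root mean squared error from 5.2 to 4.5.

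The gaps, the direction and the missing sensitivity analysis all stand. Three things weigh against acting on them.

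- The error is one only against a target that neither document sets.
- The benefit depends on the hazard shape. When the hazard falls to a third after week 40, the model is more biased at 12 months than Kaplan-Meier (+1.4 against +1.0), though its root mean squared error is still a little lower (4.3 against 4.7). Between CTs the answer comes from the assumed curve, not from data.
- It would need component-level progression-free dates, and how central review handles clinical and blood findings is left to a charter not available here.

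The plan is also not silent on timing. The SAP states the CT schedule, and SAP 4.2.2.3 provides by-visit response summaries for the Phase 2 CLL cohort, with listings and swimmer plots.

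**Conclusion.** No change follows. The planned Kaplan-Meier rates are correct for DoR as defined, namely time to documented progression or death. Read as time to actual progression, they would be high by roughly 1 to 5 points for on-treatment same-scan responders if half of progressions are caught at visits, and by at most 8.5 points if all are seen only on CT and the true 12-month rate is as low as 70%. The 95%, 85% and 70% rates, the exponential curve, the share seen at visits and the share of deaths are all assumptions. PFS behaves alike: the 12- and 18-month gaps are 16.2 and 18.3 weeks for a Cycle 7 responder, but 4.2 and 6.3 weeks for a Cycle 4 responder.

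No test, threshold or comparator uses these rates, and ORR and its power are untouched. Fewer CTs in responders for a coarser descriptive curve is a fair trade-off. Analysts may state the CT interval under the table or explore an interval-censored fit at the 24-month cut-off if events allow. The first alters no result, and the second trades a small, known direction of error for dependence on a model.
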